6.7.1.2 Adverse Events (AEs)

Adverse events (AEs) will be collected from the time of surgery until the last study visit or premature discontinuation from the study.

Treatment-emergent adverse events (TEAEs) are those AEs which worsen in severity on or after date of surgery or with onset date on or after date of surgery. AEs with missing start dates, but with stop dates either overlapping into the treatment period or missing, will be considered TEAEs. Treatment-related includes possibly or probably or definitely relationship of the event to the investigational device, procedure, anesthesia, or oncology medicine.

All AEs will be coded by System Organ Class (SOC) and Preferred Term (PT) using the Medical Dictionary for Regulatory Activities (MedDRA). Incidences of TEAEs will be tabulated by SOC and PT, cumulatively per time point (Up to Day 90, Up to Day 180, and Up to Day 360). Incidences of TEAEs will also be presented by maximum severity, seriousness, unanticipated adverse device effect (UADE) and relatedness (device or procedure related) cumulatively per time point. This includes the reporting of device revisions, reoperations, removals, supplemental fixations, or other procedures. Subjects who discontinued due to TEAEs will be summarized by SOC and PT in a separate table. Patients are counted only once in each SOC, and only once in each PT category, cumulatively per time point.

The following tables will be developed for summarizing AEs cumulatively per time point.

- Overall summary of TEAEs, it includes number of treatment-emergent adverse events, subjects with any TEAE, subjects with any serious adverse events (SAE), subjects with any severe TEAEs, subjects with any device related TEAEs, subjects with any procedure related TEAEs, subjects with any anesthesia related TEAEs, subjects with any Oncology Medicine related TEAEs, subjects with any unanticipated adverse device effect (UADE), subjects with TEAEs leading to study discontinuation and death.
- Summary of TEAEs by system organ class and preferred terms
- Summary of serious TEAEs by system organ class and preferred terms
- Summary of TEAEs by system organ class, preferred terms and maximum severity

- Summary of treatment-related TEAEs by system organ class, preferred terms (device related, procedure related, anesthesia related and oncology medicine related).
- Summary of unanticipated adverse device effect (UADE) by system organ class and preferred terms
- Deaths or discontinuations due to TEAEs by system organ class and preferred terms

All AEs, SAEs and deaths will be listed.

6.7.1.3 Physical exam

Physical examination results will be displayed in listing.

7.0 HANDLING OF MISSING VALUES

In general, for all variables only the observed data from the patients will be used in the analysis.

All patients in the ITT analysis set will be included in the primary effectiveness test as long as there are non-missing baseline values and any post baseline (days 7-14, 30, and 90) values. The MMRM provides implicit imputation of missing post-baseline values through the covariance matrix reflecting the associations among responses within patient over time.

Missing data handling for the EORTC-QLQ-BM22 is described in Section 6.6.3.2.

No imputation of values for other missing data will be performed. Data that are potentially spurious or erroneous will be examined according to standard data management operating procedures. Adverse events with missing severity will be summarized as severe. Adverse events with missing causal relationship will be summarized as related. Missing safety data will not be replaced.

8.0 INTERIM ANALYSIS

An interim MMRM analysis on change from baseline VAS to Day 90 will be carried out. In an effort to have 30 evaluable patients with VAS data at 90 days, the first 37 patients to enroll in the study will be selected for inclusion in the interim analysis. The interim analysis will be conducted once those 37 enrolled patients have all either discontinued from the study prior to the 90 day visit or have reached the 90 day visit. The purpose of this interim analysis is not to stop the trial for overwhelming efficacy, but rather to (a) potentially stop for futility; and (b) potentially increase the sample size if the mean VAS improvement from baseline to Day 90 is large but not as large as anticipated in the original sample size calculations. The interim analysis will be reviewed and validated by an independent statistician not otherwise involved in the study, who will report to the Sponsor of whether or not a sample size increase is needed, but with no other details regarding the interim results.

The null and alternative hypotheses of interest are

$$H_0: \text{mean improvement in VAS at Day 90} \leq 53.8$$

$$H_a: \text{mean improvement in VAS at Day 90} > 53.8$$

At the interim stage, the conditional power for rejecting the above null VAS hypothesis by the time of the final analysis (a planned 68 evaluable patients) will be calculated, conditioned on the interim observed data. Patient is evaluable if he/she has VAS measurement at both baseline and Day 90 visit. The conditional power will be calculated using 1000 Monte Carlo simulations via a SAS program (see the appendix 3 for the SAS program, embedded with comments describing the program). The simulation of conditional power requires an assumption of (a) the true mean change in baseline VAS at each visit; (b) the true standard deviation of the change from baseline VAS at each visit; and (c) the true within-patient correlation of VAS. These values will be estimated from the interim observed sample, and these estimated values will be used as the assumption of the true values in the conditional power simulation. Once the interim observed sample is obtained, 1000 post-interim samples will be generated assuming that 38 (i.e. 68-30) evaluable patients will be enrolled post-interim (since, again, the total evaluable sample size is 68 patients, and assume that 30 evaluable patients among the first 37 patients are in the interim analysis, actual number of evaluable patients in interim analysis will be determined with actual interim data), and each of these simulated samples will be added to the one interim observed sample to create 1000 simulated complete-study datasets of 68 evaluable patients. On each simulated dataset, the following SAS statements will be used to test the above null hypothesis:

```
proc mixed method=ml;  
  by simulation;  
  class visit subjid;  
  model CHGvas = visit baseVAS/ ddfm=kr;  
  repeated visit / type=un subject=subjid r rcorr;  
  lsmeans visit / ;  
  lsmeans estimate visit 0 0 1/lower testvalue=-53.8;  
run;
```

where the input dataset has 3 records per patient (one record per visit) where the variable CHGVAS contains the change from baseline VAS score for that patient-visit, VISIT is a categorical variable which identifies the Day 7-14, Day 30, and Day 90 assessments, baseVAS is the baseline VAS, and SUBJID is the subject ID. The interim estimated mean change from baseline VAS at Day 90, the test-statistic, and the corresponding one-sided p-value for the above-mentioned null hypothesis are obtained from the “LSMESTIMATE” statement. The proportion of simulated datasets for which the one-sided p-value is below 0.05 is the simulated conditional power. Note that the above PROC MIXED statements will be used for the final analysis once all data are collected.

If the above simulated conditional power is $\geq 80\%$ when the final evaluable sample size for the simulated samples is equal to the pre-planned number of evaluable subjects (68), the study will continue as is. If the simulated conditional power is between 10% and 50%, the study will also continue as is. If the simulated conditional power is $<10\%$, the study may be stopped for futility. If, however, the conditional power is between 50% and 80%, then the evaluable sample size

increase required to achieve 80% simulated conditional power will be calculated using the Chen-DeMets-Lan (CDL) approach⁸. Specifically, if the simulated conditional power is between 50% and 80% with a total sample of size 68 evaluable patients, then the evaluable sample size increase (from beyond the pre-planned 68) required to achieve a simulated conditional power of 80% will be determined by plugging in increasing values of post-interim sample sizes into the conditional power program, and determining the sample size at which the conditional power achieves 80%.

Under the above CDL approach, an “alpha-penalty” does not need to be made for any sample size increase in this setting as long as the maximum sample size increase required to maintain 80% power is below the bound $100*R\%$ of the original sample size, where R is calculated as follows:

$$\sqrt{1+R}(\sqrt{1+R}-1)/\sqrt{1+R-s} = t_{0.80,df}/t_{0.95,df}$$

where s is the proportion of information at the interim analysis ($s = 30/68 = 0.441$), $t_{0.80,df}$ is the 80th percentile of the tdf distribution (to correspond to the desire to achieve 80% conditional power) and $t_{0.95,df}$ is the t critical value corresponding to a one-sided alpha of 0.05 (or i.e., the 95th percentile of the tdf distribution), where df = final degrees of freedom for the final t-statistic obtained from the PROC MIXED model. The df is unknown at this time as it depends on the interim observed sample and on the simulated data, but it will be between 50 and 70. To be conservative, the df for the numerator of the above equation will be set to 70 and the df for the denominator will be set to 50. The value of $t_{0.80,df}$ and $t_{0.95,df}$ are then 0.84 and 1.68, respectively. In that case, R will be 1.08, so as long as the final evaluable sample size required to achieve 80% simulated conditional power is <108% larger than the original pre-planned evaluable sample size of 68 patients (or i.e., as long as the final evaluable sample size is <142), the evaluable sample size may be increased to maintain 80% conditional power, without requiring a penalty on the one-sided alpha, at the final analysis.

The analyses described in section 6.6.1.1 will be generated for interim analysis.

9.0 CHANGES FROM ANALYSIS METHODS PLANNED IN THE PROTOCOL

The following changes from protocol were implemented in this SAP:

1. Secondary endpoints have been identified per Section 7 of the protocol. This prioritization may vary from the study synopsis description.
2. Health economic data in protocol section 7.9.2 has been summarized in SAP sections 6.6.3.3.
3. Protocol section 7.8.6 specified “Range of motion will be assessed using ordinal variables reflecting the forward flexion, lateral elevation, external rotation, and internal rotation of the arm.” In order to reflect data collected on CRF, the range of motion measures in section 6.6.2.6 have been modified to “At each visit, five tests for range of motion are performed: Flexion, Extension, Abduction, Lateral Rotation, and Medial Rotation.”

4. Protocol section 6.3 specified that “The values of the MSTS range from 0 to 30. The values have been divided by 30 and multiplied by 100% to facilitate interpretation.” In SAP section 6.6.2.4, MSTS score is specified to be divided by 30 and multiplied by 100 to be consistent with hypothesis testing value.
5. Protocol section 7.10 listed z critical values for calculating R, and the proportion of information was 0.5. In SAP section 8, these have been updated with using t critical values and the proportion of information being 0.441.
6. Protocol section 7.10 stated that interim analysis will be performed when 30 evaluable subjects have been treated and followed for 90 days. In SAP section 8.0, this has been updated to “In an effort to have 30 evaluable patients with VAS data at 90 days, the first 37 patients to enroll in the study will be selected for inclusion in the interim analysis. The interim analysis will be conducted once those 37 enrolled patients have all either discontinued from the study prior to the 90 day visit or have reached the 90 day visit.”
7. SAP section 6.6.1.4 added a MMRM model to compare mean change from baseline of VAS score for subjects with actual fracture type with those with impending fracture type. This analysis was not originally included in the protocol.
8. Protocol section 7.8.5 specified “The number and percentage of subjects who are considered disabled, per Investigator assessment, will be presented at each visit where disability status is collected.” Summary of disability status is removed from the SAP due to sponsor request.
9. Protocol section 7.8.7 specified “The number and percentage of subjects who returned to work, and in what capacity (e.g., full-time, part-time, with limitations) will be presented at each follow-up visit”. Summary of return to work status is removed from the SAP due to sponsor request.
10. Protocol section 8.1.2 specified that the baseline values are collected at Screening and baseline visit prior to index treatment. In SAP section 4.2, baseline values for ROM are defined as measurements collected at Day7-14 visit due to no data collected at Screening and surgery visits.

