### **6.1.2 Secondary Endpoints**

The secondary endpoints, evaluated at the Day 90 Visit, include:

- The individual components of the safety endpoint
- Other secondary endpoints include:
  - Duration of index procedure and length of hospital stay
  - Activities of Daily Living score through all follow-up intervals
  - Disability status
  - Evaluation of duration of physical therapy prescription
  - Assessment of prescription and over-the-counter analgesic medication use
  - Survivability from time of index procedure to death

The safety endpoints evaluated through Day 90 also include:

1. Incidence and number of AEs.
2. Incidence and number of procedure- and device-related complications.

The secondary endpoints and safety endpoints listed above will also be examined during the extended follow up portion of the trial at Day 180 and 360.

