#### **7.8.5 Disability Status**

The numbers and percentages of subjects who are considered disabled, per Investigator assessment, will be presented at each visit where disability status is collected.

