#### **7.9.2 Health Economic Data**

Descriptive statistics for the duration of physical therapy prescription will be presented. The number and percentage of subjects who used supportive orthopedic devices post-surgery and who used prescription and over-the-counter analgesic medication will be presented. No formal statistical testing will be undertaken and no p-values will be presented.

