Version 2.0: 25 March 2016	
Clarified analysis of primary endpointClarified Enrolled subject to be consistent with protocolClarified DBL and CSR activities at all patients complete Day 90 visits, and another DBL and CSR extension by the end of studyClarified analyses will be conducted at two DBL timepointsRemoved missing data convention for incomplete diagnosis or treatment dateRemoved missing date imputation for AE and CM dateRemoved prior medication from prior/concomitant medicationAdded summary for % change of VAS values from baseline to Day 90 visit
Version 3.0: 18OCT 2016	
Clarify baseline definition, added baseline definition for ROM in Section 4.2.Clarify that only subjects with non-missing baseline and any post baseline values will be included in the analysis in Section 6.6.1.Clarify Safety success in 6.7.1.1. Radiographic success will be determined by examining device malfunction, device fracture, device removal recorded on CRF. Safety success will be determined by composite criteria on clinical and radiographic success. Statistical review meeting is removed from the text. Defined evaluable subjects in the safety summary.Clarify ranges for ROM tests, added percent change from baseline for summary.Added new analysis comparing mean VAS change from baseline at 90 Day F/U between subjects with actual and impending fracture in section 6.6.1.4

	
• Summaries for disability status and return to work status have been removed due to sponsor request
Version 3.1: 15NOV 2016	
• Removed “as the date of data extraction” from the definition of evaluable subject in safety success analysis in section 6.7.1.1.

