6.3 Demographic and Baseline Characteristics

Demographic data and subject characteristics at baseline will be summarized using descriptive summary statistics for ITT population. The demographic and baseline characteristics of age, sex, ethnicity, race, work status, occupation, disability status, history of pain, smoking history, hand dominance, primary cancer type and fracture characteristics if evident will be summarized. All demographic and baseline characteristics will be listed in full.

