- Carry out a linear transformation to convert to a 0-100 scale: $PA = \{1 - (XPA - 1) / 3\} * 100$
- If fewer than 3 of the items have a valid score treat the scale as missing.

Observed values and changes from baseline for the EORTC-QLQ-BM22 two symptom scales (PS, PC) and two function scales (FI, PA) will be summarized by visit.

6.6.3.3 Assessment of Post-Surgery Physical Therapy, Supportive Orthopedic Device and Analgesic Medication Use

At surgery visit and each post-surgery visit, subjects are asked whether physical therapy, supportive orthopedic device, or analgesic medication is prescribed. The possible answers for physical therapy and supportive orthopedic device are “Yes” or “No”. The possible answers for analgesic medication are “None”, “Over-the-counter”, and “Prescription”. At each post-surgery visit, subjects are asked whether they completed physical therapy, supportive orthopedic device, or take analgesic medication since last visit. The possible answers are the same as at surgery visit. The prescription status for physical therapy, supportive orthopedic device, and analgesic medication at surgery and each post-surgery visit will be summarized using counts and percentages. Subjects who are prescribed with “Over-the-counter” or “Prescription” for analgesic medication will be counted as “Yes” to receive analgesic prescription at each visit.

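### The SAP has no follow-up summary for two secondary endpoints listed in Protocol 6.1.2: disability status is removed without a stated scientific reason, and physical therapy duration is replaced by per-visit counts without disclosure

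*SAP*

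**What the plan says.** Protocol 6.1.2 and the synopsis give six items under other secondary endpoints. Two of them are "Disability status" and "Evaluation of duration of physical therapy prescription". Both are to be evaluated at Day 90 and again in the extended follow-up at Days 180 and 360.

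The protocol plans an analysis for each. Section 7.8.5 reads: "The numbers and percentages of subjects who are considered disabled, per Investigator assessment, will be presented at each visit where disability status is collected". Section 7.9.2 reads: "Descriptive statistics for the duration of physical therapy prescription will be presented". Section 7.8.7 adds a by-visit table of return to work, which is not on the 6.1.2 list.

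The SAP departs from this in two ways.

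- **Disability and return to work.** The revision log for Version 3.0 (18 October 2016) records: "Summaries for disability status and return to work status have been removed due to sponsor request". SAP 9.0 items 8 and 9 repeat this; for disability the entry is "Summary of disability status is removed from the SAP due to sponsor request". Baseline values are still tabulated, because SAP 6.3 includes "work status, occupation, disability status, history of pain".
- **Physical therapy.** Under SAP 6.6.3.3, prescription status at surgery and at each later visit "will be summarized using counts and percentages". The answers are Yes or No, and no duration is defined anywhere in the SAP. SAP 9.0 item 2 only points from Protocol 7.9.2 to SAP 6.6.3.3.

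**The concern.** A secondary endpoint named in the protocol is a commitment to report a result. If its summary is withdrawn for no recorded scientific or data reason, a reader cannot tell whether the outcome was uninformative, poorly collected or unfavourable. The trial has one arm and no blinding (SAP 3.4), so nothing in the design keeps accumulating outcomes from those who decide what is reported. With disability kept at baseline and dropped at follow-up, the report would show where patients started but not where they ended.

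The physical therapy change is a different problem. A count of patients with a prescription at a visit does not say how long therapy lasted, so it does not answer the listed endpoint. A reader of SAP 9.0 item 2 would think that the analysis in Protocol 7.9.2 had been carried over whole.

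**Working it through.** No sample size, power or error-rate figure is involved. The check sets the endpoint list beside the SAP.

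| Protocol 6.1.2, other secondary endpoints | Matching SAP summary |
|---|---|
| Procedure time and hospital stay | Yes, 6.6.2.2 |
| Activities of daily living | Yes, 6.6.3.2 (QLQ-BM22) |
| Disability status | Baseline only (6.3); follow-up removed (9.0 item 8) |
| Physical therapy duration | None; prescription Yes/No by visit (6.6.3.3) |
| Analgesic use | Yes, 6.6.3.3 |
| Survival after the procedure | Yes, 6.6.3.4 |

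Four of six keep a summary and two do not: 6 − 4 = 2, at each of the three reporting times (Days 90, 180 and 360).

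**Is a reason given?** SAP 9.0 gives reasons elsewhere. Item 3 changes the range-of-motion measures to match the CRF, and item 10 moves the range-of-motion baseline because nothing was collected earlier. Items 8 and 9 give only the sponsor's request.

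**Is the change disclosed?** For disability and return to work, yes, in both the revision log and SAP 9.0. For physical therapy duration, no: item 2 is a cross-reference, and the revision log has no entry on it, so the documents do not show when the change was made.

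**When was disability removed?** Version 3.0 is dated 18 October 2016. That is 370 days after SAP Version 1.0 (14 October 2015), or 370 / 30.4375 = 12.2 months. It is 286 days after Protocol Version 5.0 (6 January 2016), or 9.4 months. Planned enrolment was about 12 months. The documents give no date for the first patient, the last patient or database lock.

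**Are the data planned?** Protocol 8.3.1 to 8.3.3 and footnote 2 of both activity schedules place disability status, return to work and physical therapy prescription status at every follow-up visit. SAP 6.6.3.3 also describes a question at each post-surgery visit on whether therapy was completed, but specifies no summary of the answers.

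**How precisely could duration be recovered from visits alone?** Nominal gaps between follow-up visits are:

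- Day 7–14 to Day 30: 30 − 14 = 16 to 30 − 7 = 23 days
- Day 30 to Day 90: 60 days
- Day 90 to Day 180: 90 days
- Day 180 to Day 360: 180 days

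Visit data therefore give only an interval for the end of therapy, and a wide one late in follow-up.

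**The case against.** The case for leaving the SAP as it stands has real substance.

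- The disability and return-to-work removals are stated openly in two places, and Protocol 7.1 allows SAP amendments up to database lock. Protocol 7.8.5 sits among the secondary-endpoint analyses, so a careful reader of item 8 can work out the endpoint's status. This stands. It answers a charge of concealment, but it does not supply a reason.
- Function is still well covered beyond MSTS: return to pre-fracture mobility (SAP 6.6.2.3), range of motion (6.6.2.6) and the BM22 functional interference scale (6.6.3.2). A reader might infer that removing disability and return to work leaves MSTS as the only function outcome. The SAP contradicts that.
- Protocol 7.9 files physical therapy duration under optional analyses, and SAP 9.0 item 1 warns that the priority of secondary endpoints may differ from the synopsis. This shows that Protocol 6.1.2 and 7.9.2 disagree on status. It does not cover the change from a duration to a count.
- Protocol 4.1 anticipates fewer physical therapy prescriptions, and the retained counts speak to that directly. They do not speak to duration.
- SAP 4.1 and 6.6 promise data listings, so what is lost is the summary and not necessarily the data. Listings do not replace the promised tables.
- Planned collection is not actual collection, as item 10 shows for range of motion. If follow-up disability data were not captured, that would be a good reason, but the SAP does not give it.

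A reader might also infer from the version dates that the removal came late, after results were known, and is selective reporting. The documents do not support that: they give no enrolment or lock dates and do not say that anyone had seen these outcomes. What they support is a risk, because the reason is missing and the trial is unblinded.

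**Conclusion.** The point holds in a limited form. Two of six listed items lack a matching result at all three reporting times. Disability status was removed openly but without a scientific or data reason. Physical therapy duration was replaced by prescription counts without disclosure, and the protocol is itself inconsistent on whether that endpoint is secondary or optional. Return to work was removed alongside disability but does not add to the count of two.

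The consequence is a risk of selective reporting among descriptive secondary outcomes. The VAS and MSTS hypotheses, the type I error and the safety composite are untouched. The conclusion rests on the text of Protocol Version 5.0 and the current SAP. It assumes, without sight of the CRF, that the scheduled follow-up items were collected.

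**What to change.** 1. Reinstate the number and percentage tables of disability status and return to work by visit, as in Protocol 7.8.5 and 7.8.7, beside the baseline values already in SAP 6.3.
2. For physical therapy, report duration from CRF start and stop dates if they are captured. If not, tabulate prescribed and completed status by visit as an interval-censored, nearest-visit summary. Show deaths separately, because censoring them as if uninformative is hard to defend in metastatic disease. State in SAP 9.0 that exact duration cannot be derived.
3. Reconcile Protocol 6.1.2 and 7.9.2 on whether physical therapy duration is a secondary endpoint or an optional analysis.
4. If any item stays out, say in SAP 9.0 that an endpoint listed in the protocol was removed, why, and whether the data had been seen when the decision was made.

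The cost is a few descriptive tables and a short addition to SAP 9.0. If the scheduled items were collected, no new data are needed. The limit is precision: without dates, physical therapy duration is known only to the interval between visits.
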